¹ [1] www.consort-statement.org [2] www.strobe-statement.org [3] www.icmje.org [4] Wasserstein RL, et al. (2016), The ASA's Statement on p-Values, *The American Statistician*, 70:2, 129-133 [5] Wasserstein RL, et al. (2019), Moving to a World Beyond $p < 0.05$, *The American Statistician*, 73:sup1, 1-19 [6] Amrhein, et al. (2019) Scientists rise up against statistical significance, *Nature* 567, 305-307 [7] Editorial (2019) It's time to talk about ditching statistical significance: Looking beyond a much used and abused measure would make science harder, but better. *Nature* 567, 283-283.

Abbreviations and Definitions of Terms

Abbreviation/Acronym	Definition
AE	Adverse Event/Adverse Experience
CI	Confidence Interval
CRC	Colorectal Cancer
CRF	Case Report Form
CRP	C-Reactive Protein
eCRF	Electronic Case Report Form
FDA	Food and Drug Administration
GCP	Good Clinical Practice
GI	Gastrointestinal
GOS	Galacto-oligosaccharides
Gal	Galactose
Glc	Glucose
GSSC	Gastrointestinal Symptom and Severity Checklist
hGOS	GOS enriched with LacNAc; humanized GOS
HIPAA	Health Insurance Portability and Accountability Act
IB	Investigator's Brochure
IBD	Inflammatory Bowel Disease
IBS	Irritable Bowel Syndrome
ICF	Informed Consent Form
IL	Interleukin
INF	Interferon
IND	Investigational New Drug Application
IRB	Institutional Review Board
N	Number (typically refers to subjects)
NDA	New Drug Application
PI	Principal Investigator
QA	Quality Assurance
QC	Quality Control
SAE	Serious Adverse Event/Serious Adverse Experience
SD	Standard Deviation
SE	Standard Error
SOP	Standard Operating Procedures
TNF	Tumor Necrosis Factor
UC	Ulcerative Colitis
UP	Unanticipated Problem
WGS	Whole Genome Shotgun (Sequencing)

1. Protocol Synopsis

Study Title	Safety, Tolerability, and Biosignature of Humanized Prebiotics in Healthy Adults
Objectives	
Objective 1. Validate 15 g/day dose safety and tolerability (including absence of GI adverse effects) of GOS and hGOS in healthy adults.
 
Objective 2. Establish a biological signature of GOS and hGOS through assessment of prebiotics effects vs placebo (powdered corn syrup comprised of fructose, glucose, and an inert cellulose material that matched the consistency, color, sweetness, and taste of the prebiotics) on (i) abundance of beneficial gut bacteria and restoration of the gut microbiome saccharolytic potential, (ii) modulation of biomarkers of inflammation and (iii) evaluation of intestinal barrier function.

Target Population	
Healthy adult individuals
 
Key Inclusion Criteria: Individuals ages 18-55 with BMI of 18.5 to 32.
 
Key Exclusion Criteria:
 
 Formal diagnosis of IBD (including ulcerative colitis, Crohn's Disease) colorectal cancer, diabetes Celiac disease or IBS diagnosed by a physician Lactose intolerance as diagnosed by a hydrogen breath test C. difficile infection within 2 months Antibiotic consumption in the previous 2 months History of gastric bypass surgery Current tobacco smoker Pregnant or breastfeeding A response of 4 or 5 to questions 2 (abdominal pain), 6 (abdominal discomfort), 8 (constipation), 16 (diarrhea), 22 (abdominal distention), 26 (abdominal bloating), 31 (nausea), or 33 (vomiting).
Numbers of Participants	
Number to be recruited for screening: 55-60 participants
 
Number of eligible participants enrolled: 48 adult individuals

Clinical Phase	Pilot
Intervention	Daily oral administration of 10 - 15 g of Prebiotic galacto-oligosaccharides (GOS) or GOS enriched with lactosamine (LacNAc) for four weeks
Study Description	We will enroll 48 adult individuals (18-55 y.o.). Subjects will be assigned randomly to one of 3 groups (n = 16): GOS, hGOS or placebo (powdered corn syrup comprised of fructose, glucose, and an inert cellulose material that matched the consistency, color, sweetness, and taste of the prebiotics) to test safety and dose tolerability. The prebiotic treatment will last for 4 wk. Before the treatment (baseline) and during week 4 of the trial (after the prebiotic treatments), we will assess changes in quality and quantity in bacterial components of the gut microbiome pre- and post-treatment. Likewise, we will

	determine serum markers of inflammation, integrity of the intestinal barrier at baseline and at week 4. Participants will complete the Diet History Questionnaire (DHQ), a freely available food frequency questionnaire (FFQ) at baseline and will be asked to maintain a record of their daily diet by using a printed meal tracking diary. In addition, the PROMIS Gastrointestinal Symptom Scale will be used for potential side effect evaluation at baseline and each week for the duration of the study.
Outcome Measures	Dose safety and tolerability in healthy adults . Gut microbiome Inflammation Integrity of intestinal barrier
Study Duration	4 weeks
Subject Participation Duration	4-5 weeks
Estimated Time to Complete Enrollment	40 weeks
Statistical Analysis Plans	Data will be presented as mean \pm SEM for variables that are normally distributed, or median (IQR) for variables not normally distributed. Group means will be compared by ANOVA and post hoc tests except when data is normally distributed (a nonparametric analysis of medians will be performed using the Kruskal-Wallis test for non-normally distributed data). Chi-square tests or Fisher's exact tests will be used for incidence data. For analysis of microbiome taxonomic and functional data we will carry out Mann-Whitney-Wilcoxon matched pair tests for pairwise comparisons between time points. Unpaired Mann-Whitney-Wilcoxon tests will be used for pairwise comparisons between treatment groups. We will apply the Kruskal-Wallis test when more than two groups are compared. P values will be corrected for the total number of comparisons with false-discovery rate (FDR).

2. Introduction: Background and Scientific Rationale

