8.6. Variables Representing Treatment

A total of 45 individuals will be randomized 1:1:1 (placebo, GOS, hGOS) to treatment. Allowing for a 20% drop out rate, approximately 55 - 60 subjects will be enrolled.

9. Statistical Analysis Plans

a. Strategies that Apply to all the Specific Aims

- (1) To help ensure replicability of the research, the analysis plans will be reviewed and finalized prior to collection of data (a priori). For the specific aim, the analysis plan specifies detailed steps for obtaining estimates of population parameters (e.g intervention safety) and for making inferences.
- (2) Sensitivity analyses will be performed to assess the robustness of the major results as indicated by their sensitivity to reasonable perturbations of the choices of the methods and assumptions used. Any question about the optimal choice of methods and assumptions are best handled by relegating competing approaches to roles in the domain of sensitivity analyses. Results of the sensitivity analyses will be used to guide our level of trust in the main results. Best practices for dealing with incomplete data will depend on the documented causes of missing, censored, and coarsened values. The reasons for missing data values, drop-out, and protocol departures will have been documented in/with the database.
- (3) The plan also includes outcome-dependent exploratory analyses to generate new hypotheses.
- (4) Descriptive graphical and tabular methods will be used to characterize the participants, visualize the data, and examine relationships among variables.
- (5) To indicate precision, all statistical estimates of population parameters will be tabulated along with corresponding confidence intervals (CI) or standard errors (SE). The CI will be interpreted as the set of potential values of the population parameter that are most compatible with the observed data.
- (6) All hypothesis tests yielding p-values that are deemed to be not statistically significant will be reported as being inconclusive. The proposed statistical analysis strategy acknowledges that no p-value can reveal the plausibility, presence, truth, or importance of an association or effect-- which is consistent with the statements of the American Statistical Association [4,5], the recommendations in Nature [6,7], and guidance, such as the CONSORT Statement [1], STROBE Statement [2], and ICMJE guidance [3].²

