9.2. Aim-Specific Plans

Plans for Aim 1 (A1): Validate 15 g/day dose safety and tolerability (absence of GI adverse effects) of GOS and hGOS in healthy adults.

Method. We will report descriptive statistics for demographics, basic medical history, prescription and over the counter, and dietary supplements, including means and standard deviations for continuous variables, and percentages and ranges for categorical data. We will report the number and percent of all individuals (intent to treat) who had any adverse event (prompted or in response to an open-ended question). We will also report the number and percent of events over time, as well as the severity of the event.

Statistical analysis for A1. Data will be presented as mean \pm SD for variables that are normally distributed, or median (IQR) for variables not normally distributed. Binary/categorical outcomes will be reported as a percentage with confidence interval.

Plans for Aim 2: Establish a biological signature of GOS and hGOS through assessment of prebiotics effects vs placebo on:

(A2.1) Abundance of beneficial gut bacteria and restoration of the gut microbiome saccharolytic potential

Method. Determination of abundance of beneficial bacteria (*Bifidobacterium* and *Akkermansia* species) in the gut microbiome of treatment and placebo groups and the microbiome saccharolytic potential by Whole Genome Shotgun (WGS) sequencing⁵⁵. For assignment of saccharolytic (SAC) and non-saccharolytic (NON_SAC) phenotypes we will use the reference study by Vieira-Silva *et al.*²⁶ as described⁹.

Statistical analysis (A2.1). we will perform both exploratory analysis and statistical testing for changes in plasma cytokines. Data will be presented as mean \pm SD. To find the change of microbiome abundance under difference circumstance, Mann-Whitney-Wilcoxon matched pair tests between baseline and 4 weeks follow-up will be performed for abundance of beneficial gut bacteria in each treatment arm. To compare the change of microbiome abundance in three arms, we will apply the Kruskal-Wallis test whether the change of microbiome abundance is the same among three groups. Due to multiple testing was proposed in A2.1, p values will be corrected for the total number of comparisons with a controlled false-discovery rate (FDR)

ditching statistical significance: Looking beyond a much used and abused measure would make science harder, but better. *Nature* 567, 283-283.

(A2.2) Modulation of biomarkers of inflammation

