Rationale. High-sensitivity C-reactive protein (hs-CRP) is a recognized marker of systemic inflammation³⁴ and specific pro-inflammatory cytokines mediate interaction between immune cells and non-immune cells, contributing to the inflammatory status of the intestine^{35, 36}. Based on previous studies with probiotics and prebiotics that report potential immunomodulatory effects³⁷⁻³⁹, we decided to monitor hs-CRP, IL-1 α , IL-1 β , IL-2, IL-6, IL-8, IL-12, TNF α , and IFN γ for the duration of the clinical trial.

Method. Determination of levels of biomarkers of inflammation (IL-1 α , IL-1 β , IL-2, IL-6, IL-8, IL-12, TNF α , and IFN γ) as well as high-sensitivity C-reactive protein, a marker of low-grade inflammation (hsCRP) in serum. We will determine cytokine levels using the MCYTOMAG-70K (Milliplex) in the Advanced Analytics Core (AAC) of the CGIBD. hsCRP concentration will be measured via hsCRP ELISA (Sigma Aldrich).

Statistical analysis (A2.2). Similar to A2.1, we will perform an exploratory analysis of changes in plasma cytokines. Data will be presented as mean \pm SD. To find the change of biomarker of interest under difference circumstance, paired t-test for matched pair between baseline and 4 weeks follow-up will be performed for levels of biomarkers in each treatment arm. To compare the change of biomarker level in three arms, we will use ANOVA to test whether the change of biomarker level is the same among three groups. Due to multiple testing, p values will be corrected for the total number of comparisons with a controlled false-discovery rate (FDR)

(A2.3) Evaluation of intestinal barrier function.

Method. Blood samples will be drawn and serum will be used to quantify zonulin using the Zonulin (IDK® Zonulin) (Serum) ELISA test (Immundiagnostik AG). Zonulin is a biomarker of impaired intestinal permeability, which has been associated with various disorders^{56, 57}.

Statistical analysis (A2.3). Since A2.3 has similar data and analytic goal as A2.2, the analytic approach will be the same as what we proposed in A2.2.

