9.5. Sample Size Rationale

Tolerability: The sample size for tolerability was not determined from power analysis but based on multiple previous clinical trials conducted with GOS⁵⁸⁻⁶¹.

Microbiome: Our previous studies^{10, 11, 31, 32} conducted with a different but equivalent GOS preparation (purified prebiotics) have demonstrated a consistent and statistically significant increased abundance of the targeted beneficial bacteria: *Bifidobacterium* and *Akkermansia*. The proposed pilot study will recruit

60 subjects. After estimated dropout rate of 20%, the final subjects that will complete the subject will be N=48, which is 16 for each arm. This sample size is chosen given limited funds available with the pilot award supporting this project.

Biomarkers of inflammation: Since this is the first study, we do not have the estimate of effect size so the power cannot be computed. Additionally, due to the limitation of the funding with n=20, we do not expect to have sufficient power to detect differences over time. In that case, we will perform an exploratory analysis of changes in plasma cytokines and biomarkers of inflammation and compare the summary statistics such as mean and standard error.

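### The synopsis reports mean ± SEM where section 9.2 reports mean ± SD (a fourfold difference at 16 per arm), and neither 9.2 nor 9.5 specifies an estimate of the marker effect versus placebo

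*Combined protocol and SAP*

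**What the plan says.** The Statistical Analysis Plans row of the synopsis says data will be shown as mean ± "SEM for variables that are normally distributed, or median (IQR) for variables not normally distributed".

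Section 9.2 gives the Aim 1 rule in nearly the same sentence, but as mean ± "SD for variables that are normally distributed, or median (IQR) for variables not normally distributed". Under A2.1 it says "we will perform both exploratory analysis and statistical testing for changes in plasma cytokines" and then specifies mean ± SD. Under A2.2 it says "Similar to A2.1, we will perform an exploratory analysis of changes in plasma cytokines" and again specifies mean ± SD. A2.3 (zonulin) adopts the A2.2 approach.

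For A2.2 the planned inference is a paired t-test of baseline against week 4 within each arm, and an ANOVA of the change across the three arms, with FDR correction.

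Section 9.5 says of the inflammation markers that "we do not expect to have sufficient power to detect differences over time". It then describes an exploratory look at changes and a plan to "compare the summary statistics such as mean and standard error".

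Section 9.a, item (5), requires a confidence interval or a standard error beside every estimate of a population parameter. Aim 2 (section 3.2) is worded as the effects of the prebiotics versus placebo.

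**The concern.** There are two linked problems.

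First, SD and SEM answer different questions. SD describes how much participants vary; SEM describes how precisely a mean is known. The synopsis and section 9.2 assign different ones to the same descriptive role, both texts are current, and no order of precedence is given. The same table or figure could follow either section and look quite different.

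Second, the trial's own Aim 2 question is a contrast with placebo, and no marker-level estimate of that contrast is specified. A paired test within the GOS arm cannot separate a prebiotic effect from whatever happens to everyone over four weeks. An omnibus ANOVA says whether the three mean changes are compatible with equality, but not which arm differs from placebo or by how much. Section 9.5 expects the tests to be underpowered, so the estimates and their intervals are what a reader will have to work with. There the plan offers a mean and a standard error with no stated contrast.

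**Working it through.** **Reproducing the plan's n.** Section 9.5: "After estimated dropout rate of 20%, the final subjects that will complete the subject will be N=48, which is 16 for each arm". Check: 60 × (1 − 0.20) = 48, and 48 / 3 = 16. This reproduces.

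**Ratio of SD to SEM.** SEM = SD / √n, so SD / SEM = √n.

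- n = 16 (section 9.5, per arm): √16 = 4.00
- n = 15 (section 8.6 randomizes 45 in three arms; 45 / 3 = 15): √15 = 3.87
- n = 20 (the figure that 9.5 gives for the inflammation markers): √20 = 4.47

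The factor is about four for every n that the document states.

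**What a standard error could refer to in 9.5.** The documents give no SD and no baseline-to-week-4 correlation. I therefore work in units of the single-visit SD, take it as equal at both visits and in all arms, and assume a correlation ρ. With n = 16 per arm:

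- SE of one arm's mean at one visit = 1 / √16 = 0.25
- SE of one arm's mean change = √(2(1 − ρ)) / √16
- SE of the active-minus-placebo difference in change = √2 × the SE of the change

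| Assumed ρ | One visit | Change in one arm | Difference in change |
|---|---|---|---|
| 0 | 0.25 | 0.35 | 0.50 |
| 0.3 | 0.25 | 0.30 | 0.42 |
| 0.5 | 0.25 | 0.25 | 0.35 |
| 0.7 | 0.25 | 0.19 | 0.27 |

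Example at ρ = 0.5: √(2 × 0.5) / 4 = 0.25, and √2 × 0.25 = 0.35.

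The three standard errors are different quantities. A standard error at one visit does not give that of the change unless ρ is known. The SE of a change in one arm is smaller than that of the placebo contrast by a factor of √2. A plan that says only mean and standard error has not said which it will report.

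**Is the placebo contrast specified elsewhere?** Section 9.2 (A2.2, A2.3) has the paired t-test and the three-group ANOVA, and no pairwise estimate. The synopsis mentions post hoc tests after ANOVA, but those are tests, and 9.2 does not carry them forward. Section 9.a, item (5), says how estimates are to be accompanied but does not list which estimates will be made.

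**The case against.** The strongest reply is that little of this is a true conflict. SD for describing data and SE for an estimate can coexist, and 9.a, item (5), allows either a CI or an SE. The phrase in 9.5 directly follows a reference to changes, so the SE may well be that of the change. The synopsis is a summary, and section 9.2 already commits to SD. Formal tests are planned, with FDR correction, and none of them depends on the measure of spread.

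Much of this stands. Section 9.5 need not contradict 9.2; it is unspecific. The reply does not remove the direct contradiction between the synopsis and 9.2, or the missing placebo estimate.

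A reader might go further in three ways that the documents do not support.

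- *That 9.5 compares arms by their standard errors.* It names no arms, and the nearest stated contrast is over time.
- *That SEM bars would produce spurious effects.* The SEM bars of two arms with no true difference just touch at t = 2 / √2 = 1.41 on 30 df, p = 0.17. That describes one way of misreading a figure. No section makes overlap of bars a decision rule, and section 9.1 does not specify error bars at all.
- *That a later trial would be badly undersized because an SEM was taken for an SD.* A labelled SEM with its n returns the SD, as SD = SEM × √n.

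**Conclusion.** The point holds in two parts. The synopsis and section 9.2 prescribe different measures for the same descriptive role, a factor of 4 at 16 per arm (3.87 to 4.47 over the other sample sizes stated), with no rule of precedence. This ratio needs no assumption beyond n. On its own it would be close to editorial.

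What gives the point weight is the second part. For the inflammation markers and zonulin, the plan specifies no estimate of the effect versus placebo, although Aim 2 asks for it and the data to compute it are already being collected. The table of standard errors rests on assumed correlations and on equal SDs; it only shows that the quantities differ, and does not predict precision in this trial.

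The SEM contradiction is limited to variables treated as normally distributed, since the synopsis gives the others median and IQR. The type I error of the planned tests is not affected, and neither are the adverse-event summaries, which are numbers and percentages.

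**What to change.** 1. In the synopsis, change SEM to SD, so that description is mean and SD (or median and IQR) throughout.
2. In 9.2 (A2.2, and A2.3 by reference) and in 9.5, replace the comparison of means and standard errors with two named estimates: the within-arm change from baseline to week 4, and the active-minus-placebo difference in change for GOS and for hGOS. Give each a 95% CI. The FDR-corrected tests can stay as they are.
3. Label every figure with n and the type of interval shown.

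The cost is wording plus a little analysis. With 10 serum markers (eight cytokines, hs-CRP and zonulin) there are 10 × 3 = 30 within-arm changes and 10 × 2 = 20 differences from placebo. No extra participants, visits or assays are needed. The intervals will look wider than SEM bars. Section 9.a, item (1), commits to finalizing the analysis plan before data are collected, which is the time to make the change.

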2.1. Background Information

An undefined three-point association exists between altered gut microbiota (dysbiosis), compromised gut barrier, and disease phenotype. This relationship is well documented in animal studies but not well examined in human studies; hence a 'triangulation' is inferred based on the association between two of these three factors. A recent review of the mechanisms, measurement, and clinical implications of a "leaky gut" in humans¹ stated that studies suggest that there are non-pathological situations that may be associated with increased intestinal permeability, and these relatively minor perturbations "can be reversed with dietary, non-pharmacological approaches". *Approaches to alleviate these conditions, including prebiotics and probiotics, in human interventions are lacking.*

Galacto-oligosaccharides (GOS) are prebiotics that have an FDA Generally Regarded As Safe (GRAS) status². GOS modulate the intestinal microbiota^{3, 4} and strengthen intestinal barrier function via modulation of goblet cell function^{5, 6}. LacNAc is the major building block of gut glycoproteins and human milk oligosaccharides^{7, 8}, but its beneficial effects have not been studied as it could not be produced in enough quantities at reasonable cost until now. We have shown that short-term feeding of pure GOS increases expression of protective mucus-producing *MUC2*, decreases intestinal permeability, and reverses proportions of fecal β -galactosidases and β -glucosidases, reflecting increases in saccharolytic bacteria, including *Bifidobacterium*⁹. Likewise, GOS enriched with LacNAc, a building block of gut glycoproteins (humanized GOS, **hGOS**) decreases intestinal permeability in old mice. *Although LacNAc is a biological component of human breast milk and gut mucins, its use as a supplement has not been assessed and hence its GRAS status has not been granted yet by FDA. An IND exempt status has been obtained for this study.* GOS is also effective in the treatment of lactose intolerance^{10, 11}. Therefore, GOS and hGOS represent an attractive approach to reducing intestinal permeability, improving the gut microbiome, and reducing inflammation in older adults. Our long-term goal is to establish the safety of pure prebiotic GOS and hGOS and their effectiveness in (i) reducing intestinal permeability and inflammation, (ii) restoring the saccharolytic potential of the gut microbiome, and (iii) alleviating mild gastrointestinal manifestations and self-reported food intolerances in older adults in long-term care. The objectives of this study are (1) to validate 15 g/day dose safety and tolerability of GOS and hGOS in **healthy adults**, and (2) to establish a biological signature of GOS and hGOS through assessment of prebiotics effects vs placebo on (i) abundance of beneficial gut bacteria and restoration of the gut microbiome saccharolytic potential, (ii) modulation of biomarkers of inflammation and (iii) evaluation of intestinal barrier function.

